### 10.2. DOSE SELECTION AND PREPARATION

The rationale for selection of doses to be used in this study is provided in Sections 4.2.1 and 4.2.2.

The specific instructions for pembrolizumab (MK-3475) preparation and administration are included in the Pharmacy Manual.

Topotecan will be prepared and administered as per the approved product label or institutional standard practice.

### 10.2.1. Timing of Dose Administration

Study treatment should be administered on Day 1 of each cycle after all procedures/assessments have been completed as detailed on the Schedule of Assessments (Section 9). Study treatment may be administered up to 3 days before or after the scheduled Day 1 of each cycle due to administrative reasons.

All study treatments will be administered on an outpatient basis.

### 10.2.2. Pembrolizumab

The specific instructions for pembrolizumab (MK-3475) dose calculation, reconstitution, preparation of the infusion fluid, and administration are included in the Pharmacy Manual.

### 10.2.3. Topotecan

Topotecan will be administered as a 30 minute IV infusion daily for 5 days. Sites should make every effort to target infusion timing to be as close to 30 minutes as possible. However, given the variability of infusion pumps from site to site, a window of -5 minutes and +10 minutes is permitted (i.e., infusion time is 30 minutes: -5 min/+10 min).

Antiemetics will be administered prior to each dose of topotecan as per institutional standards.

Pegfilgrastim can be given on day 6, 7 or 8 of every cycle, as determined necessary by the investigator.

## 11. DATA AND SPECIMEN SUBMISSION, STUDY PROCEDURES

### 11.1. DATA COLLECTION AND SUBMISSION

Data collection for this study will be done through the Medidata Rave clinical data management system. Access to the study in Rave is granted through the iMedidata application to all persons with the appropriate roles assigned in AFT CTMS System.

## 12. BIOSPECIMEN COLLECTION

[figure not shown]
In order to be eligible for the study, all subjects with progressive or recurrent SCLC must provide a tumor tissue specimen. A newly acquired specimen will be preferred, although a recently-obtained ( $\leq 42$  days prior to consent) archived sample can be used if available. Patients in the pembrolizumab (MK-3475) arm will undergo a repeat biopsy while on treatment (during weeks 4 to 6 (days 29 to 42), if clinically feasible. Patients in the topotecan arm will undergo a repeat biopsy at the time of disease progression just before the cross-over to pembrolizumab, if clinically feasible.

- The AFT Biorepository at Washington University is the central laboratory to receive these samples.

Fine needle aspirates or cytologic specimens will not be accepted. Core needle or excisional biopsies, or resected tissue is required at each time point. Importantly, the specimen should not be from a previously irradiated lesion.

In addition, whole blood and peripheral blood mononuclear cell (PBMC) samples will be collected at baseline and at specified times throughout the study. Please see the biospecimen collection schema in Section 11.1 below for specific time points. Detailed information regarding the collection, processing and shipping of samples collected for screening and during the study are included in the AFT 17 Correlative Science Manual.

### 12.1. BIOSPECIMEN COLLECTION SCHEMA

## 13. CORRELATIVE STUDIES

### 13.1. IMMUNOHISTOCHEMISTRY EVALUATION

Expression of phenotypic and functional immune cell markers on tumor infiltrating cells, as well as immune signaling markers on the surface of tumor cells will be evaluated by multispectral immunohistochemistry. FFPE tumor tissue collected from pre-treatment and on-treatment biopsy will be utilized. Immunohistochemical markers may include, but not be limited to PDL-1, PD-L2, PD-1, CD3, CD4, CD8, FoxP3, CD68, MHC I and II, GITR, OX40, LAG-3 and TIM-3.

We will correlate expression of these markers to response, PFS and OS. For those patients treated in the pembrolizumab arm, pre-treatment samples also will be compared to on-treatment biopsy samples to identify the immunophenotype of response.

### 13.2. WHOLE EXOME SEQUENCING OF TUMOR AND MATCHED NORMAL FOR EVALUATION OF MUTATIONAL BURDEN AND NEOANTIGEN LANDSCAPE

Tumor DNA and matched normal DNA will be extracted for whole exome analyses. Once DNA has been obtained and extracted, we will perform massively parallel sequencing of the tumor tissue and the available matched normal tissue. Genomic DNA will be captured via solution based hybrid selection and sequenced on the Illumina HiSeq platform. Matched normal DNA also will be collected from whole blood and sequenced in conjunction with somatic tumor DNA. This is necessary to make the variant calls in next-generation sequencing assays. It is not the intent of this analysis to utilize these samples to identify germline susceptibility mutations. However, in the course of investigating somatic sequence variations, germline susceptibility variants may be suggested by comparative germline sequencing. In addition, some somatic mutations are themselves directly suggestive of a germline predisposition (e.g. *BRCA1*). See Appendix II for plan should a potentially actionable incidental finding is identified during the course of this research.

***Assessment of total somatic mutational burden:***

The somatic sequencing data will be analyzed for base mutations, insertions, fusions, deletions, copy number alterations and in all target genes. Total nonsynonymous mutation burden per tumor sample will be determined and correlated to radiographic response. Other analysis may include differential impact of individual genomic alterations and response to study therapy.

***Assessment of the neoantigen landscape:***

Utilizing whole exome sequencing, we will identify candidate neoantigenics in SCLCs and explore their associations with response to pembrolizumab therapy.

Neoantigens are modeled in silico by examining the components of antigen presentation on MHC (*antigenicity*). Expressed somatic missense mutations

are translated into pairs of short peptide strings: one including the mutation and one corresponding to the wild type sequence. *In silico* analysis is performed (for example using NetMHC (<http://www.cbs.dtu.dk/services/NetMHC-3.2/>) or similar algorithm to predict the binding affinity of a given peptide for patient specific MHC I and II. Candidate neoantigens of particular interest will be identified by having a predicted class I or II MHC binding affinity to patient-specific HLA alleles of at least 500nM.

HLA typing may be inferred using ATHLATES or determined directly using normal DNA.

### 13.3. TRANSCRIPTOME ANALYSES

Gene expression profiling of the immunologic composition of the tumor microenvironment is assessed by RNAseq. This may be performed on pre-treatment tumor, on-treatment tumor samples, as well as serially collected peripheral blood lymphocytes. RNA is extracted, quality controlled and mRNA is isolated, fragmented, purified, and undergoes whole transcriptome library preparation per protocol.

We will utilize gene expression data to evaluate changes in the tumor and tumor microenvironment between pre- and matched on-treatment (for the pembrolizumab arm) or post-treatment (for the topotecan arm) specimens that are associated with either response or resistance to study therapy.

### 13.4. PERIPHERAL BLOOD BASED STUDIES

Multiparametric flow cytometry will be performed at baseline and during treatment to assess baseline and changes in composition/activation status of lymphocyte subsets present in peripheral blood mononuclear cell preparations (PBMCs). Lymphocyte subsets to be assayed may include, but are not limited to CD3+, CD8+ and CD4+ T-cell subsets (activated; effector/memory; regulatory) and populations of those cells as defined by the expression of activation, exhaustion, or signaling markers such as, but not limited to, FoxP3, Ki67, ICOS, CTLA-4, PD-1, LAG-3, and Tim-3.

Serially collected PBMCs may also be used to screen for autologous neoantigen-specific T cell responses in the peripheral blood. Methods for doing so include combinatorial coding with peptide-MHC multimers, which permits high-throughput detection of antigen-specific T-cells to multiple potential antigens in parallel. Briefly, using synthesized peptides from candidate neoantigens as described above, large quantities of fluorochrome-labeled peptide-MHC complexes are generated such that each neoantigen is coded by a unique fluorochrome combination. Then, using conditional MHC ligands that are cleaved upon exposure to UV-light, empty, peptide-reactive MHC molecules are then exposed to autologous T-cells and reactivity of TILs to peptide-MHC complexes will be assessed and quantified by flow cytometry.

Neoantigen-specific T-cells will be isolated and may be expanded and used for future experiments.

As improvements in technology and scalability permit, alternative strategies for identifying neoantigen-specific T cells in treated patients may be explored.

### **13.5. T CELL RECEPTOR SEQUENCING**

Using serial RNA samples extracted from PBMC and tumor samples, we will comprehensively characterize their T cell receptor repertoire. We will compare their diversity and dynamics in responders versus non-responder and also assess their correlation with changes in mutational/neoantigen burden during treatment.

In order to examine all possible variable (V), diversity (D), and joining (J) segments of the T cell receptor combinations, we will first apply the 5'RACE (5' rapid amplification of cDNA end) method using a SMART (Switching Mechanism At 5' end of RNA Transcript) library construction kit (Clontech). We will perform PCR amplification of T cell receptor  $\alpha$  (TCRA) and T cell receptor  $\beta$  (TCRB) gene products with adapter-conjugated primer sets in order to prepare amplicon libraries compatible with Illumina NGS platform. The template library will then be amplified by Nextera XT index kit (Illumina) that allows barcode tagging and pooling of up to 16 samples. Subsequently, the prepared library will be analyzed using MiSeq Reagent 600-cycle kit v3 and MiSeq system (Illumina) that will generate 3-6 million T cell receptor reads per sample. The final data will be analyzed using Tcrp software or MiTCR.

In addition, we will perform similar comprehensive T cell receptor analyses for clones of neoantigen-specific T cells isolated from PBMCs and/or TILs in section 12.4 above.

## 14. DOSE AND TREATMENT MODIFICATIONS (ESCALATION/TITRATION/OTHER), CONCOMITANT MEDICATIONS, SUPPORTIVE CARE

### 14.1. DOSE MODIFICATION

#### 14.1.1. Pembrolizumab (MK-3475) Dose Modification

Adverse events (both non-serious and serious) associated with pembrolizumab (MK-3475) exposure may represent an immunologic etiology. These adverse events may occur shortly after the first dose or several months after the last dose of treatment. Pembrolizumab dosing may continue in the event of an unrelated or grade 1 adverse event. Pembrolizumab (MK-3475) must be withheld for drug-related toxicities and severe or life-threatening adverse events, as per Table 5 below. Drug-related toxicities are managed by dose delay or interruption rather than dose reduction. See Section 14.3.1 for supportive care guidelines, including use of corticosteroids.

**Table 5. Dose Modification Guidelines for Pembrolizumab Drug-Related Adverse Events**

Toxicity	Hold Treatment For Grade	Timing for Restarting Treatment	Treatment Discontinuation
Diarrhea/Colitis	2-3	Toxicity resolves to Grade 0-1	Toxicity does not resolve within 6 weeks of last dose or inability to reduce corticosteroid to 10 mg or less of prednisone or equivalent per day within 6 weeks
	4	Permanently discontinue	Permanently discontinue
AST, ALT, or Increased Bilirubin	2	Toxicity resolves to Grade 0-1	Toxicity does not resolve within 6 weeks of last dose
	3-4	Permanently discontinue (see exception below) 	Permanently discontinue
Type 1 diabetes mellitus (if new onset) or Hyperglycemia	T1DM or 3-4	Hold pembrolizumab for new onset Type 1 diabetes mellitus or Grade 3-4 hyperglycemia associated with evidence of beta cell failure	Resume pembrolizumab when patients are clinically and metabolically stable, yet discontinue treatment if patients are not improved within 6 weeks of last dose
Hypophysitis	2-4	Toxicity resolves to Grade 0-1 Therapy with pembrolizumab can be continued while endocrine replacement therapy is instituted	Toxicity does not resolve within 6 weeks of last dose or inability to reduce corticosteroid to 10 mg or less of prednisone or equivalent per day within 6 weeks
Hyperthyroidism	3	Toxicity resolves to Grade 0-1	Toxicity does not resolve within 6 weeks of last dose or inability to reduce corticosteroid to 10 mg or less of prednisone or equivalent per day within 6 weeks
	4	Permanently discontinue	Permanently discontinue
Hypothyroidism		Therapy with pembrolizumab can be continued while thyroid replacement therapy is instituted	Therapy with pembrolizumab can be continued while thyroid replacement therapy is instituted
Infusion Reaction	2 b	Toxicity resolves to Grade 0-1	Permanently discontinue if toxicity develops despite adequate premedication
	3-4	Permanently discontinue	Permanently discontinue
Pneumonitis	2	Toxicity resolves to Grade 0-1	Toxicity does not resolve within 6 weeks of last dose or inability to reduce corticosteroid to 10 mg or less of

Toxicity	Hold Treatment For Grade	Timing for Restarting Treatment	Treatment Discontinuation
			prednisone or equivalent per day within 6 weeks.
	3-4	Permanently discontinue	Permanently discontinue
Renal Failure or Nephritis	2	Toxicity resolves to Grade 0-1	Toxicity does not resolve within 6 weeks of last dose or inability to reduce corticosteroid to 10 mg or less of prednisone or equivalent per day within 6 weeks
	3-4	Permanently discontinue	Permanently discontinue
All Other Drug-Related Toxicity, excluding hematologic toxicity	3 or Severe	Toxicity resolves to Grade 0-1	Toxicity does not resolve within 6 weeks of last dose or inability to reduce corticosteroid to 10 mg or less of prednisone or equivalent per day within 6 weeks
	4	Permanently discontinue	Permanently discontinue
Hematologic Toxicity			
Thrombocytopenia associated with bleeding	3	Toxicity resolves to Grade 0-1 or baseline May increase the dosing interval by 1 week	Toxicity does not resolve within 6 weeks of last dose Permanently discontinue if associated with severe or life threatening bleeding event
Neutropenia, anemia, or thrombocytopenia	4	Toxicity resolves to Grade 0-1 or baseline May increase the dosing interval by 1 week	Toxicity does not resolve within 6 weeks of last dose Permanently discontinue if associated with any severe or life threatening event
Note: Permanently discontinue for any severe or Grade 3 drug-related AE that recurs or any life-threatening event.			
 For patients with liver metastasis who begin treatment with Grade 2 AST or ALT, if AST or ALT increases by greater than or equal to 50% relative to baseline and lasts for at least 1 week then patients should be discontinued.			
 If symptoms resolve within one hour of stopping drug infusion, the infusion may be restarted at 50% of the original infusion rate (e.g., from 100 mL/hr to 50 mL/hr). Otherwise dosing will be held until symptoms resolve and the subject should be premedicated for the next scheduled dose: Refer to Table 8 Infusion Treatment Guidelines for further management details.			
 Patients with intolerable or persistent Grade 2 drug-related AE may hold study medication at physician discretion. Permanently discontinue study drug for persistent Grade 2 adverse reactions for which treatment with study drug has been held, that do not recover to Grade 0-1 within 6 weeks of the last dose.			

If toxicity does not resolve to Grade 0-1 within 6 weeks after last infusion, study treatment should be discontinued after consultation with the Study PI. With Study Chair and AFT agreement, patients with a laboratory adverse event still at Grade 2 after 6 weeks may continue treatment in the study only if asymptomatic and controlled.

Patients who experience a recurrence of the same severe or life-threatening event at the same grade or greater with re-challenge of pembrolizumab (MK-3475) should be discontinued from study treatment.

Dosing interruptions are permitted in the case of medical / surgical events or logistical reasons not related to study therapy (e.g., elective surgery, unrelated medical events, patient vacation, and/or holidays). Patients should be placed back on study therapy within 1 week of the scheduled interruption, unless otherwise discussed with the Study Chair and AFT. The reason for interruption should be documented in the patient's study record.

**14.1.2. Topotecan Dose Modification**

Should toxicity develop, treatment should be modified rather than discontinued. Patients will be allowed to have no more than two separate dose reductions. All dose reductions are permanent.

Patients will be evaluated on Day 1 of each 21-day cycle. In the setting of grade 1 or greater toxicity, treatment will be adjusted according to the tables below. If there is an indication for treatment to be held, re-evaluation will occur 7 days later. If treatment can be resumed on day 8, there will be at least one decrease in dose level as noted below for topotecan. If treatment must be held again at day 8, there will be a decrease by two dose levels whenever treatment resumes. If treatment must be held for 22 days or more ( $\geq 6$  weeks since initiation of last cycle), the patient will be withdrawn from study.

**Table 6. Dose Reduction Guidelines for Topotecan**

Dose level	Topotecan Dose	Schedule
-1	Decrease by 0.25 mg/m  (To 1.0 mg/m  )	Days 1-5
-2	Decrease by 0.5 mg/m  from baseline (To 0.75 mg/m  )	Days 1-5

**Table 7. Dose Modification Guidelines for Topotecan Drug-Related Adverse Events**

Adverse Event	Parameters on day of treatment	CTCAE v4.0 Grade	Topotecan
Hematologic			
ANC	1000 – 1499 /mm 	Grade 2	Hold, then decrease by one dose level
	< 1000 /mm 	Grade 3 – 4	Hold, then decrease by one dose level
Hemoglobin	8.0 – 9.9 g/dL	Grade 2	No change
	< 8.0 g/dL	Grade 3 – 4	Hold, then decrease by one dose level
Platelets	75,000 – 99,000 /mm 	---	Hold
	50,000 – 74,000 /mm 	Grade 2	Hold, then decrease by one dose level
	< 50,000 /mm 	Grade 3 – 4	Hold, then decrease by one dose level
Neutropenic Fever	---	Grade 3 – 4	Off study
Infection (Documented clinically) with Grade 3 / 4 ANC	Local intervention	Grade 2	Hold, then decrease by one dose level
	IV antibiotics indicated	Grade 3 – 4	Off study
Non-Hematologic, Non-Neurologic			
Creatinine Clearance Cockcroft-Gault	$\geq 60$ ml/min	---	No change

(non CTCAE)	40-59 ml/min	---	Hold, then decrease by one dose level
	20-39 ml/min	---	Hold, then decrease by two dose levels
	< 20 ml/min	---	Off study
AST or ALT	2.6 – 5.0 x ULN	Grade 2	Hold
	> 5.0 x ULN	Grade 3 – 4	Hold, then decrease by one dose level
Total Bilirubin	1.6 – 3.0 x ULN	Grade 2	Hold
	> 3.0 x ULN	Grade 3 - 4	Hold, then decrease by one dose level
Alkaline phosphatase	2.6 – 5.0 x ULN	Grade 2	Hold
	> 5.0 x ULN	Grade 3 – 4	Hold, then decrease by one dose level
Other Non-Hematologic	---	Grade 2	No Change
	---	Grade 3	Hold, then decrease by one dose level
	---	Grade 4	Hold, then decrease by one dose level
 For patients with liver metastasis who begin treatment with Grade 2 AST or ALT, if AST or ALT increases by greater than or equal to 50% relative to baseline and lasts for at least 1 week then patients should be discontinued.			
 Excludes: alopecia, cough, dehydration, dry mouth, dry skin, dysphagia, edema, flatulence, flushing, heartburn, hemorrhoids, hiccoughs, hyper- or hypopigmentation, insomnia, nail changes, patient odor, or sweating.			

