**Table 1. Adequate Organ Function Laboratory Values**

System	Laboratory Value
Hematological	
Absolute neutrophil count (ANC)	$\geq 1,500$ /mcL
Platelets	$\geq 100,000$ / mcL
Hemoglobin	$\geq 8$ g/dL (without transfusion)
Renal	
Serum creatinine	$\leq 1.5$ X upper limit of normal (ULN)
OR	OR
Glomerular Filtration Rate (GFR)	GFR $\geq 60$ mL/min* for patient with creatinine levels $> 1.5$ X institutional ULN

Hepatic	
Serum total bilirubin	$\leq 1.5 \times \text{ULN}$ OR Direct bilirubin $\leq \text{ULN}$ for patients with total bilirubin levels $> 1.5 \text{ ULN}$
AST (SGOT) and ALT (SGPT)	$\leq 2.5 \times \text{ULN}$ OR $\leq 5 \times \text{ULN}$ for patients with liver metastases
Albumin	$\geq 2.5 \text{ mg/dL}$
*GFR should be calculated per institutional standards.	

9. Female patients of childbearing potential should have a negative urine or serum pregnancy within 72 hours of starting treatment. If the urine test is positive or cannot be confirmed as negative, a serum pregnancy test will be required.
10. Female patients of childbearing potential must be willing to an adequate method of contraception as outlined in Section 14.4.1 – Contraception for the course of the study through 120 days after the last dose of study medication (see Section 13.4.1). Patients of childbearing potential are those who have not been surgically sterilized or have not been free from menses for  $> 1$  year.  
Note: Abstinence is acceptable if this is the usual lifestyle and preferred contraception for the subject.
11. Male patients must agree to use an adequate method of contraception as outlined in Section 14.4.1 – Contraception - starting with the first dose of study therapy through 120 days after the last dose of study therapy. Note: Abstinence is acceptable if this is the usual lifestyle and preferred contraception for the subject.

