**Table 4. Study Treatment**

Drug	Dose/ Potency	Dose Frequency	Route of Administration	Regimen/ Treatment Period	Use
Pembrolizumab	200 mg	Every 3 weeks	IV Infusion	Day 1 of each 3 week cycle	Experimental
Topotecan	1.25 mg/m  Days 1 to 5	Every 3 weeks	IV Infusion	Days 1-5 of each 3 week cycle	Standard/ Control

The pembrolizumab (MK-3475) dosing interval may be increased due to toxicity.

Study treatment should begin on the day of randomization and no later than 48 hours from the date on which treatment is allocated/assigned (or 72 hours if randomization occurs on a Friday).

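### Table 1 admits patients whose stable baseline renal or liver values already lie in Table 7's topotecan hold rows, and the plan does not say how unchanged baseline values are handled

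*Combined protocol and SAP*

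**What the plan says.** **Entry (Section 7.1, Table 1).**
- Renal: creatinine up to 1.5 x ULN is enough. The GFR floor of 60 mL/min is written only "for patient with creatinine levels" above 1.5 x ULN, and GFR is calculated by whatever formula the institution uses.
- AST/ALT: up to 2.5 x ULN, or up to 5 x ULN "for patients with liver metastases".
- Total bilirubin: above 1.5 x ULN is accepted if direct bilirubin does not exceed ULN. Total bilirubin then has no cap.
- Alkaline phosphatase: no limit.

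**Topotecan modification (Section 14.1.2, Table 7).**
- Section 14.1.2 states: "Patients will be evaluated on Day 1 of each 21-day cycle". Cycle 1 is not excepted.
- Cockcroft-Gault clearance of 40-59 mL/min: hold, then one level down. At 20-39: "Hold, then decrease by two dose levels". Below 20: off study. The row is marked as outside CTCAE.
- AST/ALT 2.6-5.0 x ULN, bilirubin 1.6-3.0 x ULN and alkaline phosphatase 2.6-5.0 x ULN: hold. Higher values: hold, then one level down.
- A footnote to the AST/ALT row opens "For patients with liver metastasis who begin treatment with Grade 2 AST or ALT" and calls for discontinuation on a rise of at least 50% from baseline that lasts at least a week.
- After a hold the patient is re-evaluated at 7 days. Reductions are permanent and limited to two. "If treatment must be held for 22 days or more", which the text equates with six weeks or more from the start of the last cycle, the patient is withdrawn.

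**Start of treatment (Section 10.1).** Treatment begins on the day of randomization and "no later than 48 hours from the date on which treatment is allocated/assigned", or within 72 hours for a Friday randomization.

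**The concern.** The entry table and the dosing table use different tests for the same organ function. A patient can be properly eligible and yet, with nothing having changed, satisfy a topotecan hold row. Table 7 does not say whether a value unchanged from baseline counts, so sites must decide for themselves.

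For renal values the effect differs by arm. Table 5, which governs pembrolizumab, has no clearance row, so the same patient allocated to pembrolizumab meets no corresponding rule. In an open-label trial with 31 control patients, handling that depends on the arm can lower comparator dose intensity below the stated 1.25 mg/m2 and end control treatment for reasons unrelated to progression or to topotecan toxicity. Patients who stop without progression stay in six-weekly imaging only until they start another anticancer therapy (Section 15.1). That bears on the PFS comparison as well as on exposure.

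**Working it through.** **1. The plan's own figure.** The only plan figure that bears on this point is the power in Section 19.1, which is not disputed. With 59 and 27 events, HR 0.60 and one-sided alpha 0.10, power = Φ(√(59 × 27 / 86) × |ln 0.60| − 1.282) = Φ(4.304 × 0.511 − 1.282) = 0.820. This reproduces the stated 82%.

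**2. Renal overlap.** Cockcroft-Gault = (140 − age) × weight / (72 × creatinine), times 0.85 for women. Age, weight and ULN are assumptions (ULN 1.2 mg/dL for men, 1.1 for women). All four patients pass Table 1 on creatinine alone.

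| Patient | Creatinine, mg/dL (x ULN) | Clearance, mL/min | Table 7 row |
|---|---|---|---|
| Man, 70 y, 70 kg | 1.3 (1.08) | 70 × 70 / (72 × 1.3) = 52.4 | hold, one level |
| Man, 70 y, 70 kg | 1.8 (1.50) | 70 × 70 / (72 × 1.8) = 37.8 | hold, two levels |
| Woman, 70 y, 60 kg | 1.1 (1.00) | 0.85 × 70 × 60 / (72 × 1.1) = 45.1 | hold, one level |
| Woman, 75 y, 55 kg | 1.2 (1.09) | 0.85 × 65 × 55 / (72 × 1.2) = 35.2 | hold, two levels |

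Sensitivity to ULN: at creatinine 1.5 x ULN, with ULN from 1.0 to 1.3 mg/dL, the 70-year-old man runs from 45.4 down to 34.9 mL/min, and a 65-year-old, 60 kg woman from 35.4 down to 27.2. All are below 60. At the extreme, an 80-year-old, 45 kg woman at 1.8 mg/dL (ULN 1.2) has 17.7 mL/min, which is the off-study row. Many eligible patients are unaffected: a 60-year-old, 80 kg man at 1.2 mg/dL has 74.1 mL/min.

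**3. Liver overlap.** No assumption is needed; the limits are the documents' own. AST/ALT of 2.6-5.0 x ULN with liver metastases, total bilirubin of 1.6 x ULN or more with normal direct bilirubin, and alkaline phosphatase of 2.6 x ULN or more are all both eligible and in a row that begins with a hold.

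**4. Where the tables do agree.** The entry limits for neutrophils (1,500), platelets (100,000), hemoglobin (8 g/dL), AST/ALT without liver metastases (2.5 x ULN), the main bilirubin route (1.5 x ULN) and GFR (60 mL/min) each sit at the edge of a Table 7 hold row. The mismatch comes from the creatinine route, the alternative liver routes and the missing alkaline phosphatase limit. This looks like an oversight.

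**5. Sequence for an unchanged clearance below 60.** Table 2 schedules chemistry at screening and then from Cycle 2. Taking creatinine as measured with that panel, the row is met on Cycle 2 Day 1. The value is the same at the 7-day re-evaluation. A hold of 22 days on top of a 21-day cycle is 43 days, past the six-week limit (42 days), so the withdrawal rule applies. If a site instead resumes at a lower level without recovery, the row is met again next cycle, and Table 6 has only two levels.

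**6. If Table 7 also applies before the first dose.** A 7-day hold cannot fit the 48/72-hour start rule, and Section 20 excludes from the primary analysis patients who cancel before any protocol treatment. Each control patient lost this way is 1/31 = 3.2% of the arm. With k lost, control events are (31 − k) × 27/31 and the power formula above gives 0.800 for k = 3 and 0.784 for k = 5. The documents give no k. Exclusion that depends on the arm would matter more than the loss of power.

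**The case against.** The strongest reply is that Table 7 concerns toxicity. Its title limits it to drug-related events, Section 14.1.2 opens with toxicity that develops, and Section 17.1 treats findings at screening as medical history. This has force, and a reader who infers that eligible control patients must be held at Cycle 1 and then withdrawn goes beyond the text. No Cycle 1 chemistry is scheduled, and the 22-day rule counts from a previous cycle that does not yet exist. But Table 7's column header refers to values on the treatment day, the clearance row has no grade and needs no change from baseline, and the notes to Table 3 require acceptable results before every dose. Section 14.1.1 lets pembrolizumab continue for an unrelated event; Section 14.1.2 has no such sentence. From Cycle 2 the conflict does not depend on how Cycle 1 is read.

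A reader might also infer that the whole conflict falls on the control arm. For AST/ALT and bilirubin the documents do not support that: Table 5 also holds at Grade 2 and carries the same liver-metastasis footnote, so any contrast rests on the unrelated-event sentence alone. Table 5 also has a renal failure or nephritis row, but it is graded and drug-related, unlike Table 7's clearance row.

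Two provisions soften the problem. The AST/ALT footnote foresees patients who start at Grade 2, though the row still says to hold them. Exclusion criterion 12 lets an investigator keep out a patient with an interfering laboratory abnormality, but it is discretionary and not tied to Table 7.

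Finally, a hold or reduction is not a loss from the analysis. Patients who stop without progression stay in disease follow-up (Section 16.2.1), and those never treated still submit endpoint data (Section 16.5).

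**Conclusion.** Tables 1 and 7 contradict each other for renal values and overlap for three liver values. The renal conflict is the firmest: it follows from the stated limits, persists across the ULN values tried, and has no counterpart row in Table 5. On a literal reading, an eligible topotecan patient with a stable clearance below 60 mL/min meets a hold row from Cycle 2 onward. For AST/ALT and bilirubin the inconsistency is real but the contrast between arms is weak.

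A Cycle 1 hold, and any resulting exclusion from the primary analysis, is one reading of ambiguous text and not an explicit rule. The number of patients affected cannot be obtained from the documents; the clearance examples rest on assumed age, weight and ULN, and the power figures on an assumed k. The point should be fixed because the rules conflict and the repair is cheap. It does not show that the trial's comparison is already biased.

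**What to change.** Reconcile Table 1, Table 7 and Section 14.1.2 by amendment:
- State whether Table 7 applies before the first dose at Cycle 1 and, if so, how that fits the 48/72-hour start rule.
- State how each row for clearance, AST/ALT, bilirubin and alkaline phosphatase applies to a value unchanged from baseline, and make the AST/ALT row and its footnote agree.
- Use the same renal measure, with the same formula, in both tables.

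The sponsor's clinical team decides how the passages are reconciled; no threshold or dose rule is proposed here. The cost is amendment wording with no added visits. If the entry side is the one changed, there may be a few more screen failures.
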